- On treatment: the observation period from date of first dose of randomised NovoRapid®/faster-acting insulin aspart and no later than 7 days after the day of last dose of NovoRapid®/faster-acting insulin aspart. The on treatment observation period includes data collected up to and including 7 days after treatment discontinuation.

The primary objective, confirming the effect of treatment with meal-time faster-acting insulin aspart in children and adolescents with type 1 diabetes will be assessed using a non-inferiority approach comparing the change from baseline HbA_{1c} to meal-time NovoRapid®, where both treatments are combined with insulin degludec. More specifically the upper limit of the 95% confidence interval should be compared to a non-inferiority margin of 0.4. If it is below 0.4 non-inferiority will be considered established and the effect demonstrated.

The trial also aims to confirm the effect of treatment with post-meal faster-acting insulin aspart and to confirm superiority of meal-time faster-acting insulin aspart both in combination with insulin degludec in children and adolescents with type 1 diabetes. In order to control the family-wise type I error rate in the strong sense a hierarchical (fixed sequence) testing procedure will be deployed. This is based on a priority ordering of the null-hypotheses, and testing them in this order using the two-sided 95% confidence interval approach until an insignificant result appears. The effect is that rejection of the null hypothesis only will be confirmed for analyses where all previous null-hypotheses have been rejected in favour of faster-acting insulin aspart. This is done using a hierarchical testing procedure with three steps:

Step 1: HbA_{1c} non-inferiority of meal-time faster-acting insulin aspart versus meal-time NovoRapid® both in combination with insulin degludec

Step 2: HbA_{1c} non-inferiority of post-meal faster-acting insulin aspart versus meal-time NovoRapid® both in combination with insulin degludec

Step 3: HbA_{1c} superiority of meal-time faster-acting insulin aspart versus meal-time NovoRapid® both in combination with insulin degludec

Primary estimand

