17.1 Sample size calculation

The primary objective of the trial is to confirm the effect of treatment with meal-time faster-acting insulin aspart in terms of glycaemic control measured by change from baseline in HbA_{1c} 26 weeks after randomisation by comparing it to treatment with meal-time NovoRapid®, both in combination with insulin degludec, using a non-inferiority approach in children and adolescents with type 1 diabetes. The sample size is determined using a non-inferiority limit of 0.4%.

The trial also aims to confirm the effect of treatment with post-meal faster-acting insulin aspart and to confirm superiority of meal-time faster-acting insulin aspart, both in combination with insulin degludec in children and adolescents with type 1 diabetes. This is done using a hierarchical testing procedure with three steps:

Step 1: HbA_{1c} non-inferiority of meal-time faster-acting insulin aspart versus meal-time NovoRapid® both in combination with insulin degludec

Step 2: HbA_{1c} non-inferiority of post-meal faster-acting insulin aspart versus meal-time NovoRapid® both in combination with insulin degludec

Step 3: HbA_{1c} superiority of meal-time faster-acting insulin aspart versus meal-time NovoRapid®, both in combination with insulin degludec

The sample size is determined to ensure a sufficient power for the first step and the second step in the hierarchical testing procedure.

Power for the non-inferiority steps are based on a t-statistic under the assumption of a one-sided test of size 2.5%. A zero mean treatment difference for the comparison between meal-time faster-acting insulin aspart and meal-time NovoRapid® is expected, and for the comparison of post-meal faster-

acting insulin aspart and meal-time NovoRapid® a mean difference of 0.05% in favour of meal-time NovoRapid® is expected.

Based on experience from previous trials, and taking into account that the in trial observation period includes data collected after treatment discontinuation, the standard deviation for change in HbA_{1c} is assumed to be 1.3%. With this standard deviation, a sample size of 250 Subjects per group (750 in total) will ensure more than 93% power to show non-inferiority, given that the actual treatment difference is 0%. This sample size will ensure a power of 85% to show non-inferiority of post-meal faster-acting insulin aspart compared to meal-time NovoRapid®.

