$$m_{MI} = \frac{1}{100} \sum_{i=1}^{100} m_i, \quad SD_{MI} = \sqrt{\frac{1}{100} \sum_{i=1}^{100} SD_i^2 + \left(1 + \frac{1}{100}\right) \left(\frac{1}{100-1}\right) \sum_{i=1}^{100} (m_i - m_{MI})^2},$$

where m_i and SD_i are the estimated means and standard deviations for the 100 copies of the dataset, and m_{MI} and SD_{MI} are the pooled estimates.

- From m_{MI} and SD_{MI} , the 95% confidence interval for the treatment differences is calculated.

All 3 objectives will be addressed by treatment differences and associated 95% confidence interval obtained from the same primary statistical model described above.

Non-inferiority of meal-time faster-acting insulin aspart will be considered confirmed if the upper boundary of the two-sided 95% confidence interval is below or equal to 0.4% or equivalent if the p-value for the one-sided test of

$H_0: D > 0.4\%$ against $H_A: D \leq 0.4\%$,

is less than or equal to 2.5%, where D is the mean treatment difference (meal-time faster-acting insulin aspart minus meal-time NovoRapid[®]).

If the primary objective is confirmed the effect of treatment with post-meal faster-acting insulin aspart in terms of glycaemic control is to be investigated by showing that post-meal faster-acting insulin aspart is non-inferior to NovoRapid[®] both in combination with insulin degludec in terms of glucose lowering effect as assessed by change from baseline in HbA_{1c} 26 weeks after randomisation. This will be determined in the same way as above where treatment difference is set to (post-meal faster-acting insulin aspart minus meal-time NovoRapid[®]).

Finally, if both the primary and the first secondary confirmatory objective are fulfilled, the superiority of the meal-time faster-acting insulin aspart as compared to meal-time NovoRapid[®] will be tested in terms of glycaemic control. This will be assessed by comparing the upper limit of the

95% CI from the primary analysis to 0. If the upper 95% CI is below 0 then superiority will be confirmed.

Sensitivity analyses for the primary estimand:

- 2) The internal validity of the primary estimand will first be evaluated by repeating the primary analysis in 1), but excluding all factors and covariates except from treatment in the model. This analysis will explore the influence of the different factors and covariates. The analysis will use the in trial observation period.

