For endpoints measured over time mean values will be plotted to explore the trajectory over time. For survival endpoints, e.g. drop-out pattern, Kaplan-Meier plots are presented for each treatment.

Data collected before randomisation (Visit 14) will only be summarised descriptively.

Selected tables and figures will also be presented by age group, where age group refers to the following categorisation of age: $1 \leq \text{age} < 6$ years, $6 \leq \text{age} < 12$ years and $12 \leq \text{age} < 18$ years.

Testing strategy and estimands

The primary objective, confirming the effect of treatment with meal-time fast-acting insulin aspart in children and adolescents with type 1 diabetes will be assessed using a non-inferiority approach comparing the change from baseline HbA_{1c} to meal-time NovoRapid®, where both treatments are

combined with insulin degludec. More specifically the upper limit of the 95% confidence interval should be compared to a non-inferiority margin of 0.4. If it is below or equal to 0.4 non-inferiority will be considered established and the effect demonstrated.

The trial also aims to confirm the effect of treatment with post-meal fast-acting insulin aspart and to confirm superiority of meal-time fast-acting insulin aspart both in combination with insulin degludec in children and adolescents with type 1 diabetes. In order to control the family-wise type I error rate in the strong sense, a hierarchical (fixed sequence) testing procedure will be deployed. This is based on a priority ordering of the null-hypotheses, and testing them in this order using the two-sided 95% confidence interval approach until an insignificant result appears. The effect is that rejection of the null hypothesis will only be confirmed for analyses where all previous null-hypotheses have been rejected in favour of fast-acting insulin aspart. This is done using a hierarchical testing procedure with three steps:

Step 1: HbA_{1c} non-inferiority of meal-time fast-acting insulin aspart versus meal-time NovoRapid® both in combination with insulin degludec

Step 2: HbA_{1c} non-inferiority of post-meal fast-acting insulin aspart versus meal-time NovoRapid® both in combination with insulin degludec

Step 3: HbA_{1c} superiority of meal-time fast-acting insulin aspart versus meal-time NovoRapid® both in combination with insulin degludec

Primary estimand

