2.1 Sample size calculation

The primary objective of the trial is to confirm the effect of treatment with meal-time fast-acting insulin aspart in terms of glycaemic control measured by change from baseline in HbA_{1c} 26 weeks after randomisation by comparing it to treatment with meal-time NovoRapid®, both in combination with insulin degludec, using a non-inferiority approach in children and adolescents with type 1 diabetes. The sample size is determined using a non-inferiority limit of 0.4%.

The trial also aims to confirm the effect of treatment with post-meal fast-acting insulin aspart and to confirm superiority of meal-time fast-acting insulin aspart, both in combination with insulin degludec in children and adolescents with type 1 diabetes. This is done using a hierarchical testing procedure with three steps:

Step 1: HbA_{1c} non-inferiority of meal-time fast-acting insulin aspart versus meal-time NovoRapid® both in combination with insulin degludec

Step 2: HbA_{1c} non-inferiority of post-meal fast-acting insulin aspart versus meal-time NovoRapid® both in combination with insulin degludec

Step 3: HbA_{1c} superiority of meal-time fast-acting insulin aspart versus meal-time NovoRapid[®], both in combination with insulin degludec

The sample size is determined to ensure sufficient power for the first step and the second step in the hierarchical testing procedure.

Power for the non-inferiority steps are based on a t-statistic under the assumption of a one-sided test of size 2.5%. A zero mean treatment difference for the comparison between meal-time fast-acting insulin aspart and meal-time NovoRapid[®] is expected, and for the comparison of post-meal fast-acting insulin aspart and meal-time NovoRapid[®] a mean difference of 0.05% in favour of meal-time NovoRapid[®] is expected.

Based on experience from previous trials, and taking into account that the in trial observation period includes data collected after treatment discontinuation, the standard deviation for change in HbA_{1c} is assumed to be 1.3%. With this standard deviation, a sample size of 250 Subjects per group (750 in total) will ensure more than 93% power to show non-inferiority, given that the actual treatment difference is 0%. This sample size will ensure a power of 85% to show non-inferiority of post-meal fast-acting insulin aspart compared to meal-time NovoRapid[®].

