2.3 Primary endpoint

The primary endpoint to address all three confirmatory objectives is:

Change from baseline in HbA_{1c} 26 weeks after randomisation

Primary analysis

- 1) The primary estimand will be addressed by the below primary analysis on all Subjects included in FAS and using the in trial observation period. Note that if Subjects withdraw consent to contribute additional information or are completely lost to follow-up, actual missing data will occur. The primary analysis will be implemented as a statistical model using multiple imputation where the Subjects without any available HbA_{1c} measurements at scheduled visits will have their change from baseline HbA_{1c} value(s) imputed from the available information from the treatment the Subject has been randomised to. Note that this resembles in essence a mixed model of repeated measurements analysis. Subjects without post-randomisation measurements contribute to the analysis, as the missing values will be imputed. The analysis will be implemented as follows:

- In the first step, intermittent missing values are imputed using a Markov Chain Monte Carlo (MCMC) method, in order to obtain a monotone missing data pattern. This imputation is done for each group separately and 100 copies of the dataset will be generated.
- In the second step, for each of the 100 copies of the dataset, an analysis of variance model with region and strata as factors and baseline HbA_{1c} as covariate is fitted to the change in HbA_{1c} from baseline to week 12 for each treatment group separately. The estimated parameters, and their variances, from these models are used to impute missing values at week 12 for Subjects in each treatment group, based on region, strata, and baseline HbA_{1c}.
- In the third step, for each of the 100 copies of the dataset, missing values at week 26 are imputed in the same way as for week 12. The imputations are based on an analysis of variance model with region and strata as factors and baseline HbA_{1c} and HbA_{1c} at week 12 as covariates.
- For each of the complete data sets, the change from baseline to week 26 is analysed using an analysis of variance model with treatment, region and strata as factors, and baseline HbA_{1c} as a covariate.
- The estimates and standard deviations for the 100 data sets are pooled to one estimate and associated standard deviation using Rubin's formula:

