$$m_{MI} = \frac{1}{100} \sum_{i=1}^{100} m_i, \quad SD_{MI} = \sqrt{\frac{1}{100} \sum_{i=1}^{100} SD_i^2 + \left(1 + \frac{1}{100}\right) \left(\frac{1}{100-1}\right) \sum_{i=1}^{100} (m_i - m_{MI})^2},$$

- where m_i and SD_i are the estimated means and standard deviations for the 100 copies of the dataset, and m_{MI} and SD_{MI} are the pooled estimates.
- From m_{MI} and SD_{MI} , the 95% confidence interval for the treatment differences is calculated.

All three objectives will be addressed by treatment differences and associated 95% confidence interval obtained from the same primary statistical model described above.

Non-inferiority of meal-time fast-acting insulin aspart will be considered confirmed if the upper boundary of the two-sided 95% confidence interval is below or equal to 0.4% or equivalent if the p-value for the one-sided test of

$$H_0: D > 0.4\% \quad \text{against} \quad H_A: D \leq 0.4\%,$$

is less than or equal to 2.5%, where D is the mean treatment difference (meal-time fast-acting insulin aspart minus meal-time NovoRapid®).

If the primary objective is confirmed, the effect of treatment with post-meal fast-acting insulin aspart in terms of glycaemic control is to be investigated by showing that post-meal fast-acting insulin aspart is non-inferior to NovoRapid® both in combination with insulin degludec in terms of glucose lowering effect, as assessed by change from baseline in HbA_{1c} 26 weeks after randomisation. This will be determined in the same way as above where treatment difference is set to (post-meal fast-acting insulin aspart minus meal-time NovoRapid®).

Finally, if both the primary and the first secondary confirmatory hypotheses are fulfilled, the superiority of the meal-time fast-acting insulin aspart as compared to meal-time NovoRapid® will be tested in terms of glycaemic control. This will be assessed by comparing the upper limit of the 95% CI from the primary analysis to 0. If the upper 95% CI is below 0 then superiority will be confirmed.

Sensitivity analyses for the primary analysis addressing the primary estimand

- 2) First, the primary analysis in 1) will be repeated, but excluding all factors except treatment from the multiple imputation and analysis of variance models while still including baseline HbA_{1c} as a covariate. This analysis will explore the influence of the different factors. The analysis will use the in-trial observation period.

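### The 85% power for post-meal non-inferiority ignores the gate at step 1; through the plan's fixed sequence it is about 81%

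*SAP*

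**What the plan says.** SAP 2.1 states the aim of the sizing: "The sample size is determined to ensure sufficient power for the first step and the second step in the hierarchical testing procedure". Protocol 17.1 says the same in almost the same words. Both then list the inputs: a one-sided t-test at 2.5%, a margin of 0.4%, an SD of 1.3% for change in HbA1c, 250 Subjects per arm, and true differences of 0 (meal-time) and 0.05% in favour of NovoRapid (post-meal). Step 1 is given more than 93% power. For step 2 the SAP says "This sample size will ensure a power of 85% to show non-inferiority of post-meal fast-acting insulin aspart" and the protocol says "This sample size will ensure a power of 85% to show non-inferiority of post-meal faster-acting insulin aspart".

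The testing rule is in SAP section 2 (Testing strategy and estimands): "rejection of the null hypothesis will only be confirmed for analyses where all previous null-hypotheses have been rejected". Protocol section 17 (General considerations) has the same rule: "rejection of the null hypothesis only will be confirmed for analyses where all previous null-hypotheses have been rejected". The primary analysis text applies it to step 2 in SAP 2.3 ("If the primary objective is confirmed, the effect of treatment with post-meal fast-acting insulin aspart") and in Protocol 17.3 ("If the primary objective is confirmed the effect of treatment with post-meal faster-acting insulin aspart").

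**The concern.** The sample size is justified by reference to the hierarchical procedure, and a single unqualified figure of 85% is then given for its second step. In that procedure a post-meal result that meets the margin does not count unless the meal-time result has met it too. The probability of confirming step 2 is therefore the probability that both comparisons succeed, which cannot exceed the power of step 2 alone and is lower unless every success at step 2 comes with a success at step 1. Neither document says that the 85% leaves the gate out.

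Post-meal non-inferiority is one of three confirmatory objectives and one of the two that the trial is said to be sized for. Someone reading 85% as the chance of confirming it would be working with too high a figure.

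**Working it through.** **Inputs** (SAP 2.1; same in Protocol 17.1): n = 250 per arm, SD = 1.3, margin 0.4, one-sided 2.5%, true differences 0 (step 1) and 0.05 (step 2). Allocation is 1:1:1 (SAP 1.1), and both steps compare with the meal-time NovoRapid arm.

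**1. Reproduce the stated powers, each comparison alone.**

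SE of a difference = 1.3 × √(2/250) = 0.1163.

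- Step 1: 0.4/0.1163 − 1.960 = 1.480, so the normal power is Φ(1.480) = 93.1%. Noncentral t: 92.97% (498 df) to 93.00% (747 df).
- Step 2: (0.4 − 0.05)/0.1163 − 1.960 = 1.050, so the normal power is Φ(1.050) = 85.3%. Noncentral t: 85.2%.

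Both stated figures are recovered to rounding. The 85% is therefore the stand-alone power of step 2.

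**2. Correlation between the two comparisons.** Each difference has variance 2σ²/n. The covariance comes only from the shared NovoRapid mean and equals σ²/n. The correlation is (σ²/n)/(2σ²/n) = 0.5.

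**3. Probability that both steps succeed.**

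| Method | Both steps |
|---|---|
| Bivariate normal, Φ₂(1.480, 1.050; 0.5) | 81.6% |
| t with pooled SD, 747 df, by quadrature | 81.45% |
| Simulated three-arm trials, two-arm variance | 81.4% |
| Simulated three-arm trials, pooled variance | 81.5% |

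The result does not hinge on the exact correlation. The joint probability is 79.4% if the comparisons were independent, and it reaches 85.3% only if they were perfectly correlated.

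**4. Trials lost at the gate.** Step 2 meets the margin but step 1 does not: 85.3% − 81.6% = 3.7% from the rounded figures, 3.8% before rounding.

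**5. What could move the figure.** The planned analysis is a covariate model: the week 26 change "is analysed using an analysis of variance model with treatment, region and strata as factors", with baseline HbA1c as covariate. If 1.3 is the unadjusted SD of change, the residual SD is 1.3 × √(1 − R²). R² is an assumption here, because the documents do not give one.

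| Assumed R² | Both steps |
|---|---|
| 0% | about 81.5% |
| 5% | 83.7% |
| 8% (SD 1.247) | 85.0% |
| 15% | 88.0% |

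If 1.3 is already a residual SD, 81.5% stands. Missing data act in the other direction. SAP 2.1 expects fewer than 5% to withdraw. If a full 5% of the information were lost (about 238 per arm) with no covariate gain, step 2 alone would have 83.6% and the sequence 79.3% (normal approximation).

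**The case against.** The 85% is not a miscalculation. It is the correct power for the comparison described, and the text just before it shows how it was obtained: a t-statistic, a one-sided 2.5% test, and a separate assumed difference for each comparison. A statistician could recognise it as a per-comparison figure. The sizing sentence promises only sufficient power and sets no numerical target for the joint event, so 81% breaches no stated requirement. The SD is described as that of change in HbA1c, which reads most naturally as unadjusted, and the primary model adjusts for baseline HbA1c, region and age strata. A modest R² of 8% would bring the sequential figure back to 85%. Finally, the SAP was written with the trial under way (it follows protocol version 5.0 of January 2017 and already mentions how few children under 3 were included), so a revised planning figure changes nothing in conduct or interpretation.

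Most of this stands as fact: the per-comparison figure is right, the covariate gain is plausible, and no decision depends on the number. It does not remove the mismatch. The figure is offered in support of a claim about power within the hierarchy, it carries no label, and the plan's power basis includes no covariate gain. A gain that is not stated cannot support a stated 85%, and possible loss from missing data is left out in the same way.

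**Conclusion.** The point holds. On the plan's own assumptions, the probability of confirming post-meal non-inferiority through the fixed sequence is about 81% (81.4% to 81.6%), roughly 4 points below the stated 85%. Put as failure, the risk of not confirming it is about 18.5% (100 − 81.5) instead of about 15%. This rests on the documents' inputs and on a correlation of 0.5, which follows from the shared control, equal allocation and a common SD. It is before any gain from covariate adjustment and before any loss from missing data, neither of which can be quantified from the documents. The fault lies in what the figure is presented as measuring, not in its calculation. Step 1's power and control of the type I error are unaffected.

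**What to change.** In SAP 2.1 and Protocol 17.1, label the 93% and 85% as per-comparison (marginal) powers and add one sentence, for example: *Under the hierarchical procedure, the probability of confirming step 2 is about 81% on the same assumptions, before any gain from covariate adjustment or loss from missing data.*

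The cost is one or two sentences in each document and a slightly less favourable figure for step 2. The sample size need not change. For reference only, 85% through the sequence on the same inputs would take about 272 per arm (normal approximation).
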